APPENDIX 15 WOMEN OF CHILDBEARING POTENTIAL DEFINITIONS AND METHODS OF CONTRACEPTION

DEFINITIONS

Woman of Childbearing Potential (WOCBP)

A woman is considered fertile following menarche and until becoming post-menopausal unless permanently sterile. Permanent sterilization methods include hysterectomy, bilateral salpingectomy, and bilateral oophorectomy.

Women in the following categories are not considered WOCBP

- Premenarchal
- Premenopausal female with 1 of the following:
 - Documented hysterectomy
 - Documented bilateral salpingectomy
 - Documented bilateral oophorectomy

Note: Documentation can come from the site personnel's review of the participant's medical records, medical examination, or medical history interview.

- Postmenopausal female
 - A postmenopausal state is defined as 12 months of amenorrhea in a woman over age 45 years in the absence of other biological or physiological causes. In addition, females under the age of 55 years must have a serum follicle stimulating hormone, (FSH) level > 40 mIU/mL to confirm menopause.

Note: Females treated with hormone replacement therapy, (HRT) are likely to have artificially suppressed FSH levels and may require a washout period in order to obtain a physiologic FSH level. The duration of the washout period is a function of the type of HRT used. The duration of the washout period below are suggested guidelines and the investigators should use their judgement in checking serum FSH levels.

- 1 week minimum for vaginal hormonal products (rings, creams, gels)
- 4 week minimum for transdermal products
- 8 week minimum for oral products

Other parenteral products may require washout periods as long as 6 months. If the serum FSH level is > 40 mIU/ml at any time during the washout period, the woman can be considered postmenopausal.

CONTRACEPTION GUIDANCE FOR FEMALE PARTICIPANTS OF CHILD BEARING POTENTIAL

Any one of the approved methods of contraception (highly effective and/or less than highly effective) listed below is required during study duration and for 30 days after treatment has been discontinued.

Local laws and regulations may require use of alternative and/or additional contraception methods.

Highly Effective Contraceptive Methods That Are User Dependent
 
Failure rate of <1% per year when used consistently and correctly.^a


• Combined (estrogen- and progestogen-containing) hormonal contraception associated with inhibition of ovulation and/or implantation (These methods of contraception cannot be used by WOCBP participants in studies where hormonal contraception is prohibited)^b
– oral (birth control pills)– intravaginal (vaginal birth control suppositories, rings, creams, gels)– transdermal

• Progestogen-only hormonal contraception associated with inhibition of ovulation^b
– oral– injectable

Highly Effective Methods That Are User Independent

• Implantable progestogen-only hormonal contraception associated with inhibition of ovulation and/or implantation (This method of contraception cannot be used by WOCBP participants in studies where hormonal contraception is prohibited)^b• Intrauterine device (IUD)^c• Intrauterine hormone-releasing system (IUS) (This method of contraception cannot be used by WOCBP participants in studies where hormonal contraception is prohibited)^{b,c}• Bilateral tubal occlusion

• Vasectomized partner 
A vasectomized partner is a highly effective contraception method provided that the partner is the sole male sexual partner of the WOCBP and the absence of sperm has been confirmed. If not, an additional highly effective method of contraception should be used.

• Sexual abstinence 
Sexual abstinence is considered a highly effective method only if defined as refraining from heterosexual intercourse during the entire period of risk associated with the study treatment. The reliability of sexual abstinence needs to be evaluated in relation to the duration of the study and the preferred and usual lifestyle of the participant.
 
• It is not necessary to use any other method of contraception when complete abstinence is elected.• WOCBP participants who choose complete abstinence must continue to have pregnancy tests, as specified in Section 2.• Acceptable alternate methods of highly effective contraception must be discussed in the event that the WOCBP participants chooses to forego complete abstinence

NOTES:

- ^a Typical use failure rates may differ from those when used consistently and correctly. Use should be consistent with local regulations regarding the use of contraceptive methods for participants participating in clinical studies.
- ^b Hormonal contraception may be susceptible to interaction with the study treatment, which may reduce the efficacy of the contraceptive method. Hormonal contraception is permissible only when there is sufficient evidence that the IMP and other study medications will not alter hormonal exposures such that contraception would be ineffective or result in increased exposures that could be potentially hazardous. In this case, alternative methods of contraception should be utilized.
- ^c Intrauterine devices and intrauterine hormone releasing systems are acceptable methods of contraception in the absence of definitive drug interaction studies when hormone exposures from intrauterine devices do not alter contraception effectiveness

Less Than Highly Effective Contraceptive Methods That Are User Dependent

Failure rate of >1% per year when used consistently and correctly.

- Male or female condom with or without spermicide. Male and female condoms cannot be used simultaneously
- Diaphragm with spermicide
- Cervical cap with spermicide
- Vaginal Sponge with spermicide
- Progestogen-only oral hormonal contraception, where inhibition of ovulation is not the primary mechanism of action (This method of contraception cannot be used by WOCBP participants in studies where hormonal contraception is prohibited)

Unacceptable Methods of Contraception

- Periodic abstinence (calendar, symptothermal, post-ovulation methods)
- Withdrawal(coitus interruptus).
- Spermicide only
- Lactation amenorrhea method (LAM)

CONTRACEPTION GUIDANCE FOR MALE PARTICIPANTS WITH PARTNER(S) OF CHILD BEARING POTENTIAL.

Male participants with female partners of childbearing potential are eligible to participate if they agree to the following during the treatment and until the end of relevant systemic exposure.

- Inform any and all partner(s) of their participation in a clinical drug study and the need to comply with contraception instructions as directed by the investigator.

No additional contraceptive measures are required to be used.

COLLECTION OF PREGNANCY INFORMATION

Guidance for collection of Pregnancy Information and outcome of pregnancy on the Pregnancy Surveillance Form is provided in [Section 6.4](#) and the Appendix for Adverse Events and Serious Adverse Events Definitions and procedures for Evaluating, Follow-up and Reporting

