2 ETHICAL CONSIDERATIONS

2.1 Good Clinical Practice

This study will be conducted in accordance with Good Clinical Practice (GCP), as defined by the International Conference on Harmonisation (ICH) and in accordance with the ethical principles underlying European Union Directive 2001/20/EC and the United States Code of Federal

Regulations, Title 21, Part 50 (21CFR50). The study will be conducted in compliance with the protocol. The protocol and any amendments and the subject informed consent will receive Institutional Review Board/Independent Ethics Committee (IRB/IEC) approval/favorable opinion prior to initiation of the study. All potential serious breaches must be reported to BMS immediately. A serious breach is a breach of the conditions and principles of GCP in connection with the study or the protocol, which is likely to affect, to a significant degree, the safety or physical or mental integrity of the subjects of the study or the scientific value of the study.

Study personnel involved in conducting this study will be qualified by education, training, and experience to perform their respective task(s). This study will not use the services of study personnel where sanctions have been invoked or where there has been scientific misconduct or fraud (eg, loss of medical licensure, debarment).

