All FRP that will be treated as outpatients from consenting to the first dose of apixaban, must have a negative serum or urine pregnancy test (minimum sensitivity 25 IU/L or equivalent units of HCG) within 24 hours prior to the start of study drug.

- b. Women must not be breastfeeding
- c. FRP must agree to follow instructions for method(s) of contraception for the duration of treatment with study drug (approximately 28 days), plus 30 days (duration of ovulatory cycle) for a total of 30 days post-treatment completion. (As outlined in [Appendix 15](#))
 - i. Abstinence will be considered an acceptable form of birth control.

Men who are sexually active with FRP must agree to follow instructions for method(s) of contraception as outlined in [Appendix 15](#).

Investigators shall counsel FRP on the importance of pregnancy prevention with highly effective forms of contraception and the implications of an unexpected pregnancy. Highly effective methods of contraception have a failure rate of $< 1\%$ when used consistently and correctly. Contraceptive counseling should be provided at the time of assent or consent.

- At a minimum, subjects must agree to the use one method of highly effective contraception as listed in [Appendix 15](#).

Local laws and regulations may require use of alternative and/or additional contraception methods.

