4.5 Selection and Timing of Dose for Each Subject

A phased recruitment for this study has been done, based on the informed dose selection from the single dose PK/PD study. Recruitment began for children of ages 2 to < 18 years. Subsequently, enrollment for children 1 to < 2 years has started given that the dose selection by the sponsor [REDACTED] has been completed and endorsed by the DMC. This protocol update includes dosing for children > or equal to 1 year of age.

Subjects 1 to <18 years of age will be administered apixaban twice daily by mouth or via a NGT or GT according to weight range as per below [Table 1.2-2](#) during approximately 28 days of induction chemotherapy including asparaginase.

Table 4.5-1: Apixaban Doses for Ages 1- <18 Years of Age Under Protocol Amendment 5

Weight range	Dose
≥ 35 kg	2.5 mg twice daily
<35 to 25 kg	2 mg twice daily
<25 to 18 kg	1.5 mg twice daily
<18 to 10.5 kg	1 mg twice daily
<10.5 to 6 kg	0.5 mg twice daily

The previously communicated dosing for the body weight tier of 9 to < 12 kg has been redistributed into a 6 to < 10.5 kg weight tier and a 10.5 to < 18 kg weight tier.

Note: Study medication will be administered in accordance with the instructions provided. Subjects ≥ 5 years may be administered either 2.5 mg, 0.5 mg tablets or oral solution apixaban while subjects < 5 years and < 35 kg may be administered 0.5 mg tablets only.

Apixaban can be administered by mouth (PO) or via a NGT or GT followed with or without food approximately 12 hours apart. The oral solution should be administered with the appropriate dosing syringe provided by the Sponsor. The apixaban 2.5 mg tablet can be crushed and suspended in water or 5% dextrose in water (D5W) or apple juice or can be mixed with applesauce and promptly administered orally. Alternatively, apixaban 2.5 mg tablets can be crushed and suspended in 60 mL of water or D5W and promptly delivered through a NGT. The apixaban 0.5 mg tablets can be mixed with applesauce or can be suspended in water, apple juice, or formula and promptly administered orally.

Study medication must be initiated prior to or within 12 hours of the first dose of asparaginase or by Day 4±3 of planned 3-4 drug systemic induction chemotherapy, whichever is first. Dose modifications of study medication are not permitted. Patients may start their study medication at the same time each day.

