5 STUDY ASSESSMENTS AND PROCEDURES

5.1 Flow Chart/Time and Events Schedule

Table 5.1-1: Screening Procedural Outline ACCL1333 / CV185155			
Procedure	Consent/Screening Visit^a Day -7 to 4±3	Randomization Visit^a Day 1 to 4±3	Notes
Eligibility Assessments			
Informed Consent/Assent	X		Informed consent/assent must be signed prior to initiating any study procedures.
Inclusion/Exclusion Criteria	X	X	
Medical History	X		
Physical Measurements	X		Height, Body Weight, and calculated Body Mass Index
Catheter History	X		
Concomitant Medication Assessment	X	X	Medications taken at the time of signing the informed consent and after signing the informed consent must be recorded on the appropriate CRF page
Safety Assessments			
Full Physical Examination	X		Includes assessment of signs of venous thromboembolism or bleeding.
Vital Signs	X		Heart rate, BP, respiratory rate and temperature
Adverse Events Assessment		X	Collection of SAEs begins after signed consent; Collection of non-serious AE begins after randomization

Table 5.1-1: Screening Procedural Outline ACCL1333 / CV185155			
Procedure	Consent/Screening Visit^a Day -7 to 4±3	Randomization Visit^a Day 1 to 4±3	Notes
Laboratory Tests	X		CBC with platelets, ALT, AST, conjugated bilirubin, serum creatinine, PT (if available), aPTT and INR (Total bilirubin is acceptable if it is normal. Conjugated bilirubin should be obtained if total bilirubin is high). Renal function must be > 30% of normal for age and size. A platelet count ≥ 20 x 10 ⁹ per L must be obtained within 24 hours prior to starting apixaban. Screening labs as part of the standard of care obtained within 1 week prior to signing the informed consent can be used
Laboratory Tests during LP WBC and RBC in CSF	X	X	WBC and RBC in CSF required only once
Pregnancy Test FRP only	X		Negative serum or urine pregnancy test (minimum sensitivity 25 IU/L or equivalent units of HCG) for FRP.
Clinical Drug Supplies			
Dispense Study Drug		X	Study medication must be initiated prior to or within 12 hours of the first dose of asparaginase or by Day 4±3 of induction chemotherapy, whichever is first
Enroll via IVRS	X		
Randomize via IVRS		X	Randomization occurs between Day 1 and 4±3 of planned 3-4 drug systemic induction chemotherapy. Subjects can be enrolled and randomized during the same visit.

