^a Screening visit can occur up to 14 days prior to randomization. It can also occur at the treatment visit (Day 1 - 4±3) as long as the subject is eligible by medical history, clinical exam, and has the laboratory results back to confirm the inclusive parameters.

Table 5.1-2: Study Procedural Outline ACCL1333 / CV185155					
Procedure	During Treatment Days 7 ± 5 For in-patients only	During Treatment Days 8 ± 5, 15 ± 5, 22 ± 5	End of Treatment Day 29 ± 5 or early drug discontinuation^a	Follow-up Visit Day 35 ± 5	Notes
Concomitant Medication Assessment	X	X	X	X	If done on Day 7 do not need to repeat on Day 8
Safety Assessments					
Targeted Physical Examination	X	X	X		Includes organ systems pertinent to the subject's signs, symptoms, or adverse events, eg, assessment of signs of VTE or bleeding. If done on Day 7 do not need to repeat on Day 8
Vital Signs	X	X	X		Heart rate, BP, respiratory rate and temperature If done on Day 7 do not need to repeat on Day 8
Adverse Events Assessment	X	X	X	X	Collection of SAEs begins after signed consent Collection of non-serious AE begins after randomization
Laboratory Tests: CBC with Platelets, ALT, AST, and direct (conjugated) bilirubin	X	X	X		If done on Day 7 do not need to repeat on Day 8
Laboratory Tests during the LP RBC in the CSF		X	X		RBC in the CSF only taken at investigator defined LPs

Table 5.1-2: Study Procedural Outline ACCL1333 / CV185155					
Procedure	During Treatment Days 7 ± 5 For in-patients only	During Treatment Days 8 ± 5, 15 ± 5, 22 ± 5	End of Treatment Day 29 ± 5 or early drug discontinuationa	Follow-up Visit Day 35 ± 5	Notes
In-patient Pharmacokinetic (PK) and anti-Xa sample collection. See Section 5.5	X				For subjects receiving apixaban only. For inpatient, a pre-dose PK and anti-FXa sample may be taken 1 day prior to LP (prior to the day 7 AM dose if LP on day 8) followed by a PK and anti-FXa sample taken 1-4 hr post dose. If the subject is outpatient, follow alternate sample collection procedures.
Alternate PK sample and anti-Xa collection. See Section 5.5		X			For outpatients, random PK and anti-FXa samples may be obtained prior to LP procedures for example during the Day 8 ± 5 visit and during Day 15 ± 5 visits.
Efficacy Assessments					

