The **Screening Period** will occur after consent is obtained between Day -7 to Day 4±3 of planned 3-4 drug systemic induction chemotherapy, and will begin with a screening visit. Screening labs as part of the standard of care can be used prior to signing the informed consent. At the screening visit the IVRS system will be contacted to obtain a unique subject number. A complete medical history and a physical examination including vital signs, height, BP, and body weight, will be obtained. The screening visit laboratory studies will include: CBC with platelets, ALT, AST, conjugated bilirubin, WBC and RBC in CSF (LP prior to receiving study medication), and serum creatinine (estimated GFR), PT (if available), aPTT, and INR and serum or urine pregnancy test for FRP.

For all FRP that will be inpatients from consenting to the first dose of apixaban, it is expected that a negative pregnancy test be recorded in the subject's hospital chart at any time point from the time of hospitalization but prior to first treatment.

All FRP that will be treated as outpatients from consenting to the first dose of apixaban, must have a negative serum or urine pregnancy test (minimum sensitivity 25 IU/L or equivalent units of HCG) within 24 hours prior to the start of study drug.

Day 1 is defined as the first day of planned 3-4 drug systemic induction chemotherapy.

The Randomization visit will occur between Day 1 and Day 4±3 of planned 3-4 drug systemic induction chemotherapy. For pediatric subjects who meet all the inclusion/exclusion criteria, the IVRS system will be contacted and the subjects will be randomized.

Pediatric subjects randomized to apixaban will receive instructions about the study drug. If conditions for apixaban administration are met, study medication must be initiated prior to or within 12 hours of the first dose of asparaginase or by Day 4±3 of planned 3-4 drug systemic induction chemotherapy whichever is first. Day 1 is the first day of planned 3-4 drug systemic induction ALL chemotherapy.

For a subject who experiences a reaction to asparaginase during the infusion and has to switch to Erwinia Asparaginase during the induction chemotherapy, it is recommended that the subject continue the study treatment. The percentage of the original Asparaginase dose delivered will be recorded in the patient charter.

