5.3.4 Pregnancy tests

For females of reproductive potential (FRP), a serum or urine pregnancy test should have a minimum sensitivity of 25 IU/L or equivalent units of β HCG. All on-study pregnancy testing should follow the schedule detailed in [Table 5.1-1](#).

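### Appendix 15 accepts any one listed contraceptive method, including a condom alone, while Protocol 3.3.1 requires a highly effective one; its pregnancy-test pointer for abstinent girls also leads to no test

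*Protocol*

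**What the plan says.** **Contraception.** Protocol 3.3.1, item 3c, requires females of reproductive potential to follow the contraception instructions in Appendix 15 for about 28 days of treatment plus 30 days, and accepts abstinence. The text after 3c has investigators counsel on highly effective methods (failure rate below 1%). It then sets a floor of one highly effective method, again referring to Appendix 15 for the list.

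Appendix 15, in its guidance for female participants, states the requirement differently. Any one approved method on its lists is enough, and it says in parentheses that this covers both the highly effective and the less than highly effective groups. The second group (failure rate above 1% per year) contains condom, diaphragm, cervical cap, sponge, and a progestogen-only pill that does not act mainly by inhibiting ovulation.

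**Pregnancy testing.** Within its entry on sexual abstinence, Appendix 15 says "WOCBP participants who choose complete abstinence must continue to have pregnancy tests, as specified in Section 2". The protocol section with that number is "2 ETHICAL CONSIDERATIONS". Section 5.3.4 says "All on-study pregnancy testing should follow the schedule detailed in" Table 5.1-1, the screening table, whose entry reads "Negative serum or urine pregnancy test (minimum sensitivity 25 IU/L or equivalent units of HCG) for FRP". For outpatients, 3.3.1 adds a test "within 24 hours prior to the start of study drug". For inpatients, the screening text in Section 5.1 accepts a negative result recorded "at any time point from the time of hospitalization but prior to first treatment".

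**The concern.** Item 3c hands the working instructions on contraception to Appendix 15, so that is where site staff will look, both at entry and during treatment. A site applying its general sentence would accept a girl relying on a condom alone. A site applying the minimum in 3.3.1 would not. Two sites could treat the same girl differently, and the looser choice gives weaker protection against pregnancy during exposure to an anticoagulant.

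The testing sentence is worded as an obligation but points to a section that cannot be followed. A site reading it must guess whether it refers to tests the girl has before dosing anyway or to something further.

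**Working it through.** No arithmetic applies. The check is to set the passages side by side.

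**Contraception standard**

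| Case | Protocol 3.3.1 minimum | Appendix 15 general sentence |
|---|---|---|
| Highly effective method | met | met |
| Complete abstinence | met (3c accepts it; Appendix 15 classes it as highly effective when maintained for the whole period of risk) | met |
| Condom, diaphragm, cap or sponge alone | **not met** | **met** |
| Periodic abstinence, withdrawal, spermicide only | not met | not met (listed as unacceptable) |

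The two texts disagree only in the third row. The lower list cannot be read as describing add-on methods, because the general sentence makes one method of either group sufficient. The appendix also sits uneasily with itself: for a girl who gives up abstinence, it calls for discussion of highly effective alternatives. Its sentence about local laws allows alternative or additional methods but does not say which of the two standards governs.

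**Testing pointer**

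1. Protocol Section 2 consists of 2.1 (Good Clinical Practice), 2.2 (IRB/IEC) and 2.3 (Informed Consent). None mentions a pregnancy test.
2. No other place fits the label. Inclusion item 2 is the target population, Appendix 15 has no numbered sections, and SAP Section 2 is the study description.
3. The schedule itself is consistent. Table 5.1-1 marks the test under the consent/screening visit only. Sections 3.3.1 and 5.1 add pre-dose timing. The laboratory row of Table 5.1-2 reads "Laboratory Tests: CBC with Platelets, ALT, AST, and direct (conjugated) bilirubin", and that table has no pregnancy-test row. The visit descriptions from Day 7 to Day 35, in the synopsis and in Section 5.1, list none either.
4. Section 5.3.3 mentions a pregnancy test when applicable, and Section 5.3 allows extra testing on medical grounds. Neither sets a day.

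The tables, the visit texts and Section 5.3.4 therefore agree on pre-dose testing only. The Appendix 15 sentence is the one piece that does not connect to them.

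**Reach into the analysis.** The relevant protocol deviations in SAP 7.2.1, which define the Evaluable population, include nothing on contraception or pregnancy testing. The ITT and safety populations contain all randomized subjects.

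**The case against.** On contraception, the two rules can both be obeyed: a girl who meets 3.3.1 also meets Appendix 15. The minimum stands among the inclusion criteria, and the text closing 3.3.2 insists that every eligibility criterion be met in full. On that reading a girl using only a condom is ineligible, and the appendix merely needs tidying. This is fair for a reader who compares the two texts. It does not remove the error, because 3.3.1 itself sends the site to Appendix 15 for instructions, the appendix then states a lower requirement, and no rule of precedence is given.

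On testing, Section 5.3.4 covers all on-study tests and sends them to the screening table. The word *continue* in Appendix 15 can simply mean that abstinence does not exempt a girl from the pre-dose tests. This objection stands.

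A reader might go further and infer that a mandatory pregnancy test during treatment was dropped from the schedule, or that the plan needs one at Day 15. The documents do not support either. Nothing outside the broken pointer implies an on-treatment test. The plan relies on pre-dose testing, contraception through 30 days after treatment, extra testing when medically indicated, discontinuation rules for pregnancy (Section 3.5) and reporting within 24 hours (Sections 6.1.1 and 6.4). These girls also receive multi-drug induction chemotherapy throughout, so stopping apixaban after a positive test would remove only one exposure. An added test is a choice open to the sponsor.

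**Conclusion.** The contraception conflict is a real error in the text: Appendix 15 accepts methods that fall below the minimum in 3.3.1. The testing pointer is also wrong, but it is close to clerical, because the rest of the protocol gives one consistent pre-dose schedule.

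Severity is minor. The matter concerns participant safety and consistent eligibility. It touches no endpoint, analysis or sample size, and pregnancy reporting is intact. The documents do not say how many girls would rely on a lower-tier method or on abstinence, so no count is offered. The conclusion does not depend on one: it rests on the wording alone, and neither the relevant rows nor the cited sections show any sign of redaction or extraction loss.

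**What to change.** 1. In the general sentence of Appendix 15, replace the opening so that it reads: *One highly effective method from the list below (complete abstinence included) is required*. Leave the stated duration unchanged (the study period and 30 days after treatment ends).
2. Head the less-than-highly-effective list *Not sufficient alone*.
3. In the abstinence entry, replace the pointer to Section 2 with: *Section 5.3.4 and Table 5.1-1 (abstinence does not exempt a subject from the pre-dose tests in 3.3.1)*.
4. Only if the sponsor did intend testing during treatment, name the visit in Table 5.1-2 and in Section 5.3.4. A serum or urine test at Day 15 ± 5, when blood is already drawn, is one option.

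Items 1 to 3 are wording changes confined to Appendix 15. They add no procedure and leave the schedule and the analysis unchanged. Item 4, if chosen, would add one test per girl concerned and one table row.
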